This is a cluster randomized controlled trial to investigate the effect of our contraceptive decision support tool on women's contraceptive continuation, as well as on their experience of contraceptive counseling, measured both quantitatively and qualitatively. In addition, we will collect quantitative and qualitative data to determine the impact of the implementation of this tool on the experience of providers and the clinics in which they work. Data collection will occur in three stages: 1) pre-intervention phase, 2) intervention phase, including follow-up of patients for seven months, and 3) post-intervention phase. For phase 1, immediately before implementing the contraceptive decision support tool, we will collect audio recordings of contraceptive counseling visits. For phase 2, we will randomize at the provider level to usual care or use of the intervention. For phase 3, we will conduct audio recordings of contraceptive counseling visits with providers in the intervention arm, as well as performing interviews of intervention providers and focus groups with clinic staff. We will use best practices for the conduct and reporting of this type of trial as detailed in the CONSORT guidelines.

III. Study Procedures

As described, this study has three main phases, outlined below. All study procedures will be conducted by UCSF study staff or UCSF study volunteers.

A. Pre-Intervention Phase Procedures

In the pre-intervention visit recording phase, we will recruit patients at the study clinics prior to implementing the intervention. Subsequently, providers will be randomized into the control or intervention arm of the study.

1. Pre-Intervention Audio Recordings

The procedure for provider participants is as follows:

- The study will be discussed at staff meetings or individually, as determined by each clinic.
- Each potential participant will then be contacted individually to have their questions answered and determine if they are willing to consent to participate. Study staff will obtain written consent for the pre-study visit recording phase and the study intervention phase at this time.
- After enrolling in the study, each provider will conduct 2-3 family planning visits in the usual fashion as are performed at the clinic with patients participating in this phase of the study.
- During these visits, the conversation between patient and provider will be recorded on a secure voice recorder.

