- The recordings from these visits will be transcribed on a computer by a HIPAA-compliant transcription service.

Study Protocol

Patient Centered Support for Contraceptive Decision-Making: A Cluster Randomized Controlled Trial of a Contraceptive Decision-Support Tool

November 22, 2016

- After completing three visits, each provider will complete a survey about their demographic characteristics and the Maslach Burnout Inventory.

The procedure for patient participants is as follows:

- After being screened and consented by study staff, each patient will complete a short demographic survey (**Note:** This survey was not added to study procedures until 11/4/15, when a minor modification detailing it was approved) and have a family planning visit in the usual fashion as is performed at the clinic with providers participating in the study. As described above, the conversation between patient and provider will be recorded on a secure voice recorder during these visits, and the visits will be transcribed.

2. Randomization

After the pre-intervention phase and before the intervention phase, the provider participants will be randomized into intervention and control arms, stratified by clinic. Providers will be randomized using a random number table, clustered by each clinic. [name] will create a random number table using Stata 13's "ralloc" randomization module and blinded study IDs provided by study staff. The decision support tool intervention will then be introduced in a short orientation to the providers randomized to the intervention arm.

B. Intervention Phase Procedures

Study staff role: UCSF Research Assistants will track all recruitment activity using the clinic-specific Recruitment Tracking Log daily. Weekly totals will be tallied each Friday afternoon. At each recruitment shift in each clinic, there should be one UCSF Research Assistant (RA) who conducts eligibility and consent processes, and, if possible, one volunteer or Patient Stakeholder Representative who assists the RA with completing tracking logs, the time study, and managing iPads and other study equipment. Time study data will be collected in this phase the same as in the pre-intervention phase: patient arrival time, tool start and end time (if applicable), visit start time with clinician, and visit end time.

The procedure for provider participants is as follows:

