Specific Aim 2: We have estimated that audio recording 2-3 patient encounters at each time point (before and after implementation of the intervention) for each of the providers randomized to the intervention will allow us to achieve saturation and to meaningfully compare the pre- and post-intervention period.

Specific Aim 3: We will conduct focus groups at each of the four clinics involved in the study, and will conduct semi-structured interviews of each of the providers randomized to the intervention. For our quantitative measures, we estimate we will have the ability to detect a less than 0.5 SD difference in consultation time and total clinic visit time. For comparison of burnout among providers, our sample size will be 24, with 12 in each group, and therefore will have limited power. In order to optimize power, we will estimate treatment effects on the final score controlling for the baseline value. Using this measure, we anticipate having 80% power to detect a 0.5 to 1.1SD differences on each of the sub-scales of the Maslach Burnout Inventory, depending on with within-provider correlation of these responses.

C. Methods of Analysis

Patient and provider stakeholders will be involved in an iterative manner in all stages of planning of analyses and in data interpretation.

[IR-1] Data required for primary analyses will be inspected, cleaned, and locked before primary analysis is begun. Data checks will include examination of descriptive statistics for plausibility (e.g. plausible

Study Protocol

Patient Centered Support for Contraceptive Decision-Making: A Cluster Randomized Controlled Trial of a Contraceptive Decision-Support Tool

November 22, 2016

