We will assess imbalance by treatment assignment using cross-tabulations and comparisons of within group means and medians. Inference for balance on provider covariates will use chi-squared, Fisher's exact, t, and Wilcoxon tests as appropriate, while differences in patient characteristics will be assessed using mixed effects models with fixed effects for clinic and random effects for provider. [IR-3] Primary analyses of treatment effects will be intention-to-treat, according to treatment assignment, and without regard to use of the tool or seeing an intervention provider. Treatment effects will be estimated using mixed effects linear, logistic, proportional odds, and multinomial models, with fixed effects for clinic and random effects for provider.

Missing data. [MD-1] Missing data will have been minimized by active follow-up of participants. [MD-4] Missing data rates for primary and secondary outcomes as well as important covariates will be reported, in combination with summaries of the reasons for missingness, including dropout and pregnancy. [MD-2] All analyses will handle missing data using 20-fold multiple imputation of missing outcomes, based on iterative chained equations. [MD-3] Summary effect estimates, averaged over the 20 imputed datasets, as well as confidence intervals and p-values, will be calculated using standard methods that account for imputation error.

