Specific Aim 2: For this aim, we will be assessing the effect of the intervention on counseling at the cluster (i.e., provider) level. We will use Dedoose software to analyze the audio recordings using modified grounded theory, with the coding performed by [name], [name], and [name], with input from patient stakeholder representatives. This coding will focus on the presence or absence of shared decision making and patient engagement in the decision making process. In conducting this coding, we will use concepts drawn from observational measures of shared decision making, including the OPTION scale and the Four Habits Coding Scheme, as well as insight into the counseling process gained through our previous observational study, to identify our initial thematic structure. We will perform iterative coding, with discussions between coders, the PI, and patient stakeholders to clarify concepts and resolve ambiguities. We will then, again in collaboration with stakeholders, qualitatively explore the extent to which the providers altered their behaviors following implementation of the intervention using memo writing, and ultimately compiling these into results.

Specific Aim 3: In order to determine the effect of the intervention on the experience of providing family planning care at the level of both the clinic and the provider, we will perform both qualitative and quantitative analyses. Quantitative analyses, including comparing consultation time and total clinic visit time for patients in the intervention and control group, will use similar methods to those described in Aim 1. We will also compare scores on each sub-scale of the Maslach Burnout Inventory (emotional exhaustion, depersonalization, and personal accomplishment), controlling for baseline values, between providers randomized to the intervention and those randomized to the control group in both bivariate

Last updated November 22, 2016

and multivariate analyses, again controlling for clustering by clinic. In addition, we will conduct a sensitivity analysis controlling for any imbalanced pre-randomization characteristics (e.g., age) that predict outcomes, using changes in the coefficient for the intervention as the criterion for covariate inclusion in the adjusted model. Thematic analysis of interview and focus group transcripts and recordings will again be performed using Dedoose software, using an iterative and collaborative process of coding as described in Aim 2.

Additional Analyses

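### The Aim 3 time analyses leave out each provider's pre-randomisation visit times. Using them is cheap and may improve precision, by an amount that depends on an ICC the plan does not state.

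*SAP*

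**What the plan says.** **Collection.** Protocol III.A.1 states that "each provider will conduct 2-3 family planning visits in the usual fashion" after enrolling. Protocol III.B then states: "Time study data will be collected in this phase the same as in the pre-intervention phase: patient arrival time", followed by tool use, visit start and visit end. Protocol III.A.2 fixes the order: "After the pre-intervention phase and before the intervention phase, the provider participants will be randomized into intervention and control arms, stratified by clinic". Read together, both arms have provider-level times recorded before allocation.

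**Analysis.** Under Methods of Analysis, Specific Aim 3, the SAP says that "comparing consultation time and total clinic visit time for patients in the intervention and control group, will use similar methods" to Aim 1. The Aim 1 models are mixed models "with fixed effects for clinic and random effects for provider", with no baseline outcome term. Protocol VII.C says the same. The SAP's provider covariates for Aim 3 are age, race/ethnicity and professional degree. The burnout subscales, in the same paragraph as the time outcomes, are compared with control for baseline. Protocol VII.B gives the reason for that choice: to make the most of limited power.

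**Power.** For the time outcomes Protocol VII.B says only: "we estimate we will have the ability to detect a less than 0.5 SD difference in consultation time and total clinic visit time". It gives no ICC for them.

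**The concern.** Arm is allocated to 24 providers, not to patients. A stable tendency of some providers to run long or short visits therefore enters the error of the arm comparison, and more patients per provider do not remove it. A pre-randomisation measure of each provider's pace could take out part of that error, and the plan appears to hold one without using it.

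At stake are the width of the confidence intervals for consultation time and total clinic visit time, and whether the stated detectable difference is secure. These outcomes bear on whether clinics can absorb the tool, so an imprecise result would be a real loss. The primary outcome is not affected.

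**Working it through.** **Inputs from the documents.** There are 24 providers, 12 per arm, with about 32 patients each (758/24 = 31.6), in four clinics. Tests are two-sided at 5% with 80% power (Protocol VII.B). Each provider has 2-3 pre-intervention visits, taken as k = 2.5. Times are taken on the visit day, so the 20% loss to follow-up is not applied.

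**Assumptions.** Provider ICC for time 0 to 0.20; correlation r of a provider's true mean time between phases 0.7 to 1; equal numbers of patients per provider; outcome SD of 1.

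**1. Formula checked against the plan's own figures.** With 758 × 0.8 = 606 patients, the detectable difference is 2.802 × √(4 × design effect / 606). Design effects of 1.3 and 1.7 give 0.26 and 0.30, against 0.25 and 0.31 in the plan's table. The formula is therefore close to the one used. The time figure is only a bound with no ICC behind it, so it cannot be reproduced as a point value.

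**2. Unadjusted analysis.** Variance of a provider mean: v0 = ICC + (1 − ICC)/32. Detectable difference: 2.802 × √(4·v0/24).
- ICC 0.075, the largest provider ICC in the plan's table for any outcome: v0 = 0.075 + 0.925/32 = 0.104, difference 0.37 SD (0.39 SD using t).
- ICC 0.165: v0 = 0.165 + 0.835/32 = 0.191, difference 0.50 SD.
- With noncentral t on 24 − 4 − 1 = 19 df, 0.50 SD is reached at an ICC of about 0.145.

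**3. Adjusting for the provider's mean pre-intervention time.** Variance of the baseline mean: vb = ICC + (1 − ICC)/2.5. Share of v0 explained: R² = (r·ICC)²/(v0·vb). The slope has to be estimated from the provider means, which costs a factor of 1 + 1/17 and one df. So v1 = v0(1 − R²)(18/17), on 18 df. Adjustment lowers the variance only when R² exceeds 1/18, or about 0.056.

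Worked case, ICC 0.20: v0 = 0.20 + 0.80/32 = 0.225 and vb = 0.20 + 0.80/2.5 = 0.52.
- r = 1: R² = 0.04/(0.225 × 0.52) = 0.342, and v1/v0 = 0.658 × 18/17 = 0.697, or 30% better.
- r = 0.7: R² = 0.49 × 0.342 = 0.168, and v1/v0 = 0.832 × 18/17 = 0.881, or 12% better.

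| Provider ICC | Power for 0.5 SD, unadjusted | Variance change, r = 1 | Variance change, r = 0.7 | Power, adjusted (r = 0.7 to 1) |
|---|---|---|---|---|
| 0 | >99% | +6% | +6% | >99% |
| 0.027 | >99% | +3% | +4% | >99% |
| 0.05 | 98% | −2% | +2% | 98% |
| 0.075 | 95% | −7% | −0.4% | 95-96% |
| 0.10 | 90% | −12% | −3% | 91-93% |
| 0.15 | 79% | −22% | −8% | 82-88% |
| 0.20 | 69% | −30% | −12% | 74-83% |

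A plus sign means a loss of precision. A simulation with 4 clinics of 6 providers and r = 1 agrees. The ratio of adjusted to unadjusted interval width was 1.03 at ICC 0. With 2 and 3 baseline visits respectively, it was 0.98 and 0.96 at ICC 0.075, and 0.91 and 0.87 at ICC 0.15.

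**The case against.** The strongest reply is that the gain is not assured. The provider ICCs that the plan reports for other outcomes run from about 0 to 0.075. Over that range the adjustment does between slight harm and slight good, and unadjusted power for 0.5 SD is already 95% or more. This stands, and it rules out saying that precision is being given up for free. Those ICCs, however, belong to patient-reported and choice outcomes and do not bound the ICC for time.

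The covariate is also weak, and this stands too. It averages 2-3 visits by other patients. Those visits were audio-recorded, and the intervention-phase procedures list no recording. Total clinic time depends on clinic flow as well as provider pace. At one clinic, by the SAP's own note, consultation time spans two staff. All of this points to r below 1. In addition, the pre-intervention times rest on one sentence in Protocol III.B; the pre-intervention steps themselves do not list a time study.

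The burnout comparison is imperfect. Burnout has one value per provider at each time point and admittedly limited power, whereas time has some 758 patient-level values. Even so, the arm effect on time is limited by the same 24 providers.

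Finally, Aim 3 already has a sensitivity analysis for imbalanced pre-randomisation characteristics that predict outcomes. Its inclusion rule is a change in the intervention coefficient, which addresses imbalance. A balanced but strong predictor would be left out, so the clause does not recover precision.

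**Conclusion.** The point holds as a modest, low-cost improvement to the two Aim 3 time outcomes. The trade is lopsided in its favour. At a provider ICC of 0.075 or below, power for 0.5 SD moves by about one point at most. At 0.15 to 0.20, where the claim of detecting under 0.5 SD would fail on the t calculation, power rises from 79% to 82-88% and from 69% to 74-83%. These figures rest on assumed ICCs and between-phase correlations, 2.5 baseline visits, and equal numbers of patients per provider.

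A reader might infer three stronger things that the documents do not support:
- **That the analysis is biased or invalid.** Providers are randomised and the unadjusted mixed model is a sound choice.
- **That provider variation is known to dominate the error.** Its share of v0 is nil at ICC 0, 47% at 0.027 (0.027/0.0574) and 89% at 0.20 (0.20/0.225), and the ICC for time is not given.
- **That the 0.5 SD claim is wrong.** It holds up to an ICC of about 0.145 to 0.165, and nothing in the documents shows that time exceeds that.

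**What to change.** First confirm from the time-study logs that pre-intervention times exist for providers in both arms. Then pre-specify their use in the SAP's Aim 3 time models, in one of two ways:
- Add each provider's mean pre-intervention time as a provider-level covariate: consultation time in one model, total visit time in the other, on the same scale as the outcome if it is transformed. State in advance how a provider without baseline times is handled, for example the clinic mean plus an indicator.
- Model both phases jointly, with the arm effect only in the intervention phase and provider effects allowed to differ between phases. This limits the loss when the ICC is small and needs no rule for missing baseline times.

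Keep the unadjusted model as a sensitivity analysis. In Protocol VII.B, state the ICC assumed for the claimed detectable difference.

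The cost is SAP wording, a sentence in the sample-size section, and about one of 19 provider-level degrees of freedom. No new data are needed. The downside is a slight loss of precision (variance up by at most about 6%) if the provider ICC is below about 0.05, or somewhat higher if provider effects are unstable between phases.
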